Clarification of Maternal Inclusion Criterion 4.11: To be eligible to enroll in IMPAACT P1110, participating infants had to be enrolled within 48 hours of birth. The protocol team recognized that source documentation of past HIV test results might not be available at the delivery site and that there might be difficulty in obtaining this documentation within the infant enrollment window of 48 hours after delivery. For this reason, the team included the stipulation in the protocol section 4.11 that HIV test results “documented in the clinical record from past testing may be used to satisfy the criteria for documentation of HIV-1 infection.” Documentation in the medical record that the diagnosis of HIV infection had previously been done using in-country standard of care diagnostic tests could be used to document HIV infection, qualifying the mother as “known to be HIV infected,” and therefore additional HIV testing as part of study procedures would not be required. An additional pragmatic factor, which further made the medical record documentation of past HIV positive test results an inclusion criterion was the situation that for women known to be HIV positive for some duration of time and on cART, they might have such low viral load that test results from re-confirming HIV infection could take longer than 48 hours, making it either impossible to enroll the infant or making maternal test results of no usefulness, being obtained after the baby is already on dosing. The algorithm for newly diagnosing HIV would be the less useful approach for a woman known to be HIV positive and medically managed for a period of time prior to study entry.

Definitions

“Known” to be HIV infected: can be documented in the medical clinic file at the research site and may include the following: 1) maternal subject is documented to be HIV positive in the medical record per the usual designation at the site, either on or starting prescribed treatment with cART (combination Anti-Retroviral Treatment) for the current pregnancy; 2) based on available medical records, or per her history obtained at the research site, from a referring clinic documented by mail (electronic or other), or phone contact with the referring prescribing healthcare provider.

“Medical record” can include: Mobile paperwork carried throughout the pregnancy as a mother gets treatment in one or more clinics; patient file hard-copy or electronic copy in the research clinic or from another clinic which notes the HIV status of the mother; or other medical record that is normally accepted by the research site.

“HIV test results” documented in the clinical record for “known” HIV positive women: the standard method of designation will be confirmed by the research site. This may include the designation of RVD positive=Retroviral Disease Positive. This designation is routinely used in some countries to document positive HIV test on the Prenatal Cards. This is done to protect the confidentiality of the HIV status of women where stigma and discrimination are potential barriers to their health care.

In summary, “HIV testing documentation required for mothers known to be HIV-infected”: For mothers known to be HIV-infected (as defined above), testing obtained and documented per the local in-country health department standard of care applicable to the research site (e.g. SOC using 2 separate tests and samples, without naming them) are sufficient for meeting the requirement of HIV-1 testing documentation in the medical record as clarified under part (i) in Section 4.11. After noting the HIV positive designation in the maternal medical record, per the health department guidelines for the site, if two samples and two timepoints are used, no further HIV testing is needed for enrollment. The HIV testing documentation algorithm only applies for mothers identified as HIV infected at the time of labor or in the immediate postpartum period, as clarified under part (ii) in Section 4.11.

Implementation

The modification included in this Letter of Amendment will be incorporated into the next protocol amendment as specified below. Additions to the text are indicated in bold; deletions are indicated by strike-through.

- 1. Section 4.11, Maternal Inclusion Criteria, is clarified regarding the required source documentation for mothers known to be HIV infected versus mothers diagnosed at the time of labor or in the immediate postpartum period. Additions to the text are indicated in bold. Furthermore, formatting changes have been made separating the first paragraph after “Documentation of HIV infection” into three paragraphs with added text shown in bold. The first paragraph applies to both groups of mothers, whereas the second paragraph is clarified as only applying to mothers who are known to be HIV infected (clarified under i). The third paragraph (newly added) and all remaining text under Section 4.11 is clarified as only applying to mothers who are diagnosed at the time of labor or in the immediate postpartum period (clarified under ii).*

4.11 Mother is either **i) known to be HIV-1 infected prior to labor (testing obtained and designated per local SOC in the medical record and either on or recently started CART prior to delivery** or **ii) identified as HIV-1 infected at the time of labor or in the immediate postpartum period.**

Documentation of HIV infection **for (i) and (ii):**

Documentation of HIV-1 infection is defined as positive results from two samples (whole blood, serum, or plasma) collected at different time points. **This can occur at enrollment or can be historical and documented by a notation of HIV positivity in the maternal medical record for women known to be HIV positive before delivery.**

(i): Results documented in the clinical record from past testing may be used to satisfy the criteria for documentation of HIV-1 infection. **No further testing for HIV is needed for this group of mothers.**

(ii): For mothers identified as HIV-1 infected at the time of labor or in the immediate postpartum period the following testing algorithm should be applied.

If both samples are tested using antibody tests, at least one of the samples must be tested in a laboratory that operates according to Good Clinical Laboratory Practice (GCLP) guidelines and participates in an appropriate external quality assurance program. If nucleic acid testing is used, at least one test must be performed in a CLIA-certified (US sites) or VQA-certified (non-US) laboratory. For tests performed in other (non-GCLP-compliant or non-VQA-certified) settings,

adequate source documentation including the date of specimen collection, date of testing, test performed, and test result must be available.

Sample #1 must be tested using any of the following:

- Up to two rapid antibody tests from different manufacturers or based on different principles and epitopes.
- One EIA OR Western Blot OR immunofluorescence OR chemiluminescence
- One quantitative HIV RNA PCR (above the limit of detection of the assay)
- One HIV DNA PCR
- One qualitative HIV RNA PCR
- One total HIV nucleic acid test

Note: Confirmatory testing (Sample #2) may be pending at the time of enrollment of the mother-infant pair. If maternal confirmatory testing is negative, the infant will be removed from active dosing but will be followed for safety as part of the study.

Sample #2 must be tested using any of the following:

- Rapid antibody test. If this option is used in combination with two rapid tests for Sample #1, at least one of the three rapid tests must be FDA-approved, and the third rapid test must be from a third manufacturer or based on a third principle or epitope.
- One EIA confirmed by Western Blot OR immunofluorescence OR chemiluminescence
- One quantitative HIV RNA PCR (above the limit of detection of the assay)
- One HIV DNA PCR
- One qualitative HIV RNA PCR
- One total HIV nucleic acid test

Clarification Memorandum #2 for:

IMPAACT P1110

A Phase I Trial to Evaluate the Safety and Pharmacokinetics of Raltegravir in HIV-1-Exposed Neonates at Risk of Acquiring HIV-1 Infection

Version 2.0, dated 18 January 2017

IND # 77,787

DAIDS ES # 11891

Clarification Memorandum Date: 15 June 2017

Summary of Clarifications

This Clarification Memorandum (CM) clarifies that infant exclusion criterion 4.43 applies to all infant participants, including Cohort 2 RAL-exposed participants as well as Cohort 1 RAL-naïve, Cohort 1 RAL-exposed, and Cohort 2 RAL-naïve. The specification of RAL-naïve was a typo in Version 2.0, and inconsistent with the intention of Section 4.5 Disallowed Medications.

Implementation

Institutional Review Board/Ethics Committee (IRB/EC) approval of this CM is not required by the study sponsor prior to implementation; however, sites may submit it to IRBs/ECs for their information or, if required by the IRBs/ECs, for their approval prior to implementation. The clarifications included in this memorandum will be incorporated into the next full protocol amendment. Modifications are shown below, using strikethrough for deletions and bold type for additions.

Section 4.4, Infant Exclusion Criteria, page 34, is clarified to emphasize that the infant exclusion criteria apply to all infants.

4.43 For Cohort 2 ~~RAL-naïve~~ and Cohort 1 (RAL-naive and RAL-exposed): Receipt of disallowed medications (phenytoin, phenobarbital, rifampin)

Clarification Memorandum #1 for:

IMPAACT P1110

A Phase I Trial to Evaluate the Safety and Pharmacokinetics of Raltegravir in HIV-1-Exposed Neonates at Risk of Acquiring HIV-1 Infection

Version 2.0, dated 18 January 2017

IND # 77,787

DAIDS ES # 11891

Clarification Memorandum Date: 08 February 2017

Summary of Clarifications

This Clarification Memorandum (CM) removes the pre-dose monitoring call and the post-dose monitoring call from the Early Discontinuation visit for Cohort 2, as participants at this visit will be off study drug and no longer being dosed.

This CM also clarifies that Appendix V-A, Sample Informed Consent for Cohort 1 (Closed), will not be used in P1110 Version 2.0, as Cohort 1 is closed to accrual, all Cohort 1 participants are no longer in follow-up and have exited the study.

Implementation

Institutional Review Board/Ethics Committee (IRB/EC) approval of this CM is not required by the study sponsor prior to implementation; however, sites may submit it to IRBs/ECs for their information or, if required by the IRBs/ECs, for their approval prior to implementation. The clarifications included in this memorandum will be incorporated into the next full protocol amendment.

In Appendix II-B: Infant Schedule of Evaluations for Cohort 2, Column for Early Discontinuation Visit, Rows for Pre-dose monitoring and Post-dose monitoring:

Pre-dose monitoring	X
Post-dose monitoring	X

IMPAACT P1110

**A Phase I Trial to Evaluate the Safety and Pharmacokinetics of Raltegravir
in HIV-1-Exposed Neonates at Risk of Acquiring HIV-1 Infection**

A Study of the International Maternal Pediatric Adolescent
AIDS Clinical Trials Network (IMPAACT)

Sponsored by:

ARV	Antiretroviral
AST	Aspartate aminotransferase
AUC	Area under the curve
BID	Twice a day
cART	Combination antiretroviral therapy
CI	Confidence interval
DAIDS PRO	Division of AIDS Protocol Registration Office
DMC	Data Management Center
DNA	Deoxyribonucleic Acid
EAE	Expedited adverse event
EC	Ethics Committee
FTC	Emtricitabine
GCLP	Good Clinical Laboratory Practice
GM	Geometric mean
HAART	Highly active antiretroviral therapy
HIV	Human immunodeficiency virus
IMPAACT	International Maternal Pediatric Adolescent AIDS Clinical Trials Network
IRB	Institutional Review Board
LAR	Legally authorized representative
LDMS	Laboratory Data Management System
NAT	Nucleic acid test
NFV	Nelfinavir
NVP	Nevirapine
OHRP	Office for Human Research Protections
PID	Patient Identification Number
PK	Pharmacokinetic
PMTCT	Prevention of Mother-to-Child Transmission
RAL	Raltegravir
RE	Regulatory entity
RNA	Ribonucleic Acid
RSC	Regulatory Support Center
SES	Subject enrollment system
SID	Study Identification Number
UDP	Uridine diphosphate
UGT	Uridine diphosphate glucuronyl transferase
ZDV	Zidovudine

SCHEMA

A Phase I Trial to Evaluate the Safety and Pharmacokinetics of Raltegravir in HIV-1-Exposed Neonates at Risk of Acquiring HIV-1 Infection

- DESIGN: Phase I, open label, non-comparative dose-finding study
- SAMPLE SIZE: Approximately 50 infants in order to accrue a minimum of 32 pharmacokinetic (PK) evaluable HIV-1-exposed infants, and their mothers. Cohort 1 will enroll a minimum of 12 PK evaluable infants and Cohort 2 will enroll a minimum of 20 PK evaluable infants.
- Note: Cohort 1 RAL-naïve, Cohort 1 RAL-exposed, and Cohort 2 RAL-naïve groups were fully accrued under protocol Version 1.0. Cohort 2 RAL-exposed group will be opened to accrual under protocol Version 2.0 and will enroll a minimum of 8 PK evaluable infants.
- POPULATION: HIV-1 exposed full-term infants (aged ≤ 48 hours in protocol Version 1.0 and ≤ 60 hours in protocol Version 2.0) assessed as risk of acquiring HIV-1 infection and their mothers. Two groups of infants will be enrolled in each Cohort according to infant *in-utero* exposure to maternal raltegravir (RAL):
- RAL-naïve (infants born to mothers not receiving RAL prior to delivery) and
 - RAL-exposed (infants born to mothers who received at least one dose of RAL within 2 – 24 hours prior to delivery).
- REGIMEN:
- Cohort 1: Raltegravir as oral granules for suspension administered at two time points: as a single dose within 48 hours of birth in addition to standard of care ARV for PMTCT prophylaxis, with a second single dose administered at 7-10 days of life.
- Cohort 2: Raltegravir as oral granules for suspension initiated in RAL-naïve infants within 48 hours of birth and in RAL-exposed infants between 12 and 60 hours of birth, as outlined below, in addition to standard of care ARV for PMTCT prophylaxis.
- 1.5 mg/kg once daily during Days 1–7 of life (week 1)
 - 3.0 mg/kg twice daily during Days 8-28 of life (weeks 2-4)
 - 6.0 mg/kg twice daily during Days 29-42 of life (weeks 5-6)
- Based on ongoing interim analysis of pharmacokinetic data and safety information, raltegravir dosing may be modified in the range of 1.5 mg/kg to 6 mg/kg per dose. Dosing frequency may also be modified from once to twice daily, reaching a maximum daily dose of 12 mg/kg/day.

STUDY DURATION: Infants will be followed for 24 weeks after birth. Women will be followed until discharge from the labor and delivery unit.

PRIMARY OBJECTIVES:

1. To evaluate the safety and tolerability through 6 weeks of life of raltegravir oral granules for suspension when administered during the first 6 weeks of life with standard PMTCT ARV prophylaxis to infants exposed to HIV-1 assessed at risk of infection.
2. To evaluate the pharmacokinetics of raltegravir oral granules for suspension during the first 6 weeks of life along with standard PMTCT ARV prophylaxis.
3. To determine an appropriate dose of raltegravir oral granules for suspension for use in neonates and infants during the first 6 weeks of life.

SECONDARY OBJECTIVES:

1. To assess safety and tolerability of raltegravir oral granules for suspension through 24 weeks of life when administered during the first 6 weeks of life with standard PMTCT ARV prophylaxis to infants exposed to HIV-1 assessed at risk of infection.
2. To investigate the relationship between neonatal raltegravir elimination and UGT1A1 genotype, and whether there is an association of UGT1A1 (*28/*28) and SLCO1B3 (rs2117032-C/T) with hyperbilirubinemia.

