RAL dosing in Cohort 1 may be modified in the range of 1.5 mg/kg to 6 mg/kg per dose. The PK results and safety will be assessed through regular team monitoring (done at least every 4 weeks) and at full cohort accrual to ensure that the individual RAL concentrations are in the target range (not exceeding C_{max} of 19.63 μM and not exceeding an AUC₁₂ of 63.05 $\mu\text{M}\cdot\text{hr}$) and that there

are no life-threatening toxicities probably or definitely related to RAL administration. Based on team assessment of the PK data and review of safety information, the dose may be modified within the stated range for the subsequent participants entering into Cohort 1.

All Cohort 1 infants will have a history, physical examination, and hematology and chemistry laboratory evaluations performed at the time of dosing for each of the two doses, and follow-up visits at 2 weeks, 6 weeks and 24 weeks of life.

Pharmacokinetic sampling for infants in Cohort 1 will include the following:

Dose 1 (within 48 hours of birth) Intensive PK: Pre-dose, 1-2 hours post-dose, 4-8 hours post-dose, 12 (± 1) hours post-dose, and 24 (± 1) hours post-dose.

Day 3-4 Single Random PK: One random PK sample will be obtained with laboratory evaluations on Day 3-4 of life.

Dose 2 (7-10 days of life) Limited PK: Pre-dose, 1-2 hours post-dose and 24 (± 1) hours post-dose.

*Note: For the 12 and 24 hour PK sampling time points, it is necessary to collect blood samples within the window of ± 1 hour for the accurate calculations of PK parameters of raltegravir. However, in the event that a sample collection in this window is not possible, the sample should be obtained within ± 2 hours and this deviation from the sampling instructions should be recorded.

Cohort 2:

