5.1 Drug Regimens, Administration, and Duration

5.11 Regimen

Cohort 1: HIV-1 exposed full-term infants

For RAL-naïve (unexposed) infants: RAL 2 mg/kg oral granules for suspension as a single dose within 48 hours of birth in addition to standard of care ARV for PMTCT prophylaxis (refer to *Appendix III, Raltegravir Weight Band Dosing Table for Oral Granules for Suspension*).

For RAL-exposed infants: RAL 1.5 mg/kg oral granules for suspension as a single dose within 48 hours of birth in addition to standard of care ARV for PMTCT prophylaxis (refer to *Appendix III, Raltegravir Weight Band Dosing Table for Oral Granules for Suspension*).

For all Cohort 1 infants (RAL-naïve and RAL-exposed infants): Administer a second single dose of RAL 3 mg/kg oral granules for suspension in addition to standard of care ARV for PMTCT prophylaxis (refer to tables in Appendix III) on day 7 to 10 of life.

Cohort 2: HIV-1 exposed full-term infants

For RAL-naïve (unexposed) infants: RAL oral granules for suspension, provided as follows in addition to standard of care ARV for PMTCT prophylaxis (refer to tables in Appendix III): First Dose to be administered within 48 hours of life:

- 1.5 mg/kg once daily during Days 1-7 of life (week 1)
- 3.0 mg/kg twice daily during Days 8-28 of life (weeks 2-4)
- 6.0 mg/kg twice daily during Days 29-42 of life (weeks 5-6)

For RAL-exposed infants. First dose to be administered between 12 and 60 hours of life (refer to tables in Appendix III):

- 1.5 mg/kg once daily during Days 1-7 of life (week 1)
- 3.0 mg/kg twice daily during Days 8-28 of life (weeks 2-4)
- 6.0 mg/kg twice daily during Days 29-42 of life (weeks 5-6)

The reference weight to be used for each dose, and throughout the duration of that dose, is shown in the Table 10 below. The doses are calculated at 3 time points during the 6 weeks:

1. Initial dose based on birth weight;
2. At day 6-9 of life study visit; and
3. At day 28-32 of life study visit.

Note: Intent is to minimize the number of dose adjustments while receiving study treatment.

Table 10
Weight for Weight Bands (Cohort 2 RAL-exposed) in Appendix III

RAL dose regimen	Weight to be used for Appendix III weight bands
1.5 mg/kg once daily	Birth Weight Note: First dose administered between 12 and 60 hours of life
3.0 mg/kg twice daily	Weight on Day 6-9 of Life Study Visit (Note: if infant has lost weight during first week of life, use birth weight for dose calculation)

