6.0 mg/kg twice daily	Weight on Day 28-32 of Life Study Visit

NOTE: If dose adjustment is required for Cohort 1 and Cohort 2 based on pharmacokinetic data, this will be communicated by the protocol team to sites. A new prescription will be required for the site pharmacist. Refer to Appendix III for dosing tables of RAL oral granules for suspension based on 1.5, 2, 3, 4, 5, and 6mg/kg Daily or Twice Daily.

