6.2 Study Management Plan

The Data Management Center (DMC) will maintain a web page informing sites as to the availability of enrollment slots per cohort. The protocol team, including the co-chairs, medical officers, pharmacist, and pharmacologist, will respond to sites who contact the team with questions regarding toxicity management, dosing, or other issues within one business day. Team responses will include the entire team.

Sites will be given 7 days to respond to queries to allow the team to meet Merck data delivery requirements. Sites will be contacted by the protocol data manager or co-chairs regarding any query responses or data issues that are outstanding after 7 days.

All RAL dose modifications will be recommended by the protocol team. See Section 6.21 for information on dose modifications for Cohorts 1 and 2. The protocol team will review the PK data for each participant as part of an on-going evaluation of the dosing regimen to determine whether a dose adjustment is required. The study team will conduct an extensive review of the data obtained from participants enrolled in Cohort 1 before opening enrollment for Cohort 2. Dose recommendations for Cohort 2, and supporting dose finding data from Cohort 1, must be approved by the Medical Officers, IMPAACT representatives and Merck representatives. If all agree, Cohort 2 opens to enrollment. If there is disagreement among IMPAACT, Merck and/or the study team, a Study Monitoring Committee (SMC) will be

appointed to review the data understanding that Cohort 2 will not open without Merck approval. See Section 8.51 for more details on SMC monitoring of study data and progress.

The P1110 team will notify sites of any change in dose and/or dosing frequency through an appropriate mechanism. Dosing tables found in Appendix III will be used for dosing changes and are based on weight bands.

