APPENDIX III

RALTEGRAVIR WEIGHT BAND DOSING TABLES FOR ORAL GRANULES FOR SUSPENSION

Note: Dosing Tables A through F will not be used in protocol Version 2.0 and therefore have been removed.

Dosing Tables G-I reflect reconstitution for suspension 10 mg/mL. Refer to section 5.11 for the dosing regimen (i.e. once or twice daily).

Table G. Dose of 1.5 mg/kg using RAL Oral Granules for Suspension 10 mg/mL

Weight Band (kg)	1.5 mg/kg	Volume (mL)
	Dose in (mg)	Volume to Administer
2 to <3	4 mg	0.4 mL
3 to <4	5 mg	0.5 mL
4 to <5	7mg	0.7 mL

Table H. Dose of 3 mg/kg using RAL Oral Granules for Suspension 10 mg/mL

Weight Band (kg)	3 mg/kg	Volume (mL)
	Dose in (mg)	Volume to Administer
2 to <3	8 mg	0.8 mL
3 to <4	10 mg	1mL
4 to <5	15 mg	1.5 mL

Table I. Dose of 6 mg/kg using RAL Oral Granules for Suspension 10 mg/mL

Weight Band (kg)	6 mg/kg	Volume (mL)
	Dose in (mg)	Volume to Administer
2 to <3	20 mg	2 mL
3 to <4	25 mg	2.5 mL
4 to <5	30 mg	3 mL

Note: The Tables J-M are included for potential future dose adjustments. Refer to section 5.11 on dosing schedule (i.e., once or twice daily).

Table J. Dose of 2 mg/kg using RAL Oral Granules for Suspension 10 mg/mL

Weight Band (kg)	2 mg/kg	Volume (mL)
	Dose in (mg)	Volume to Administer
2 to <3	5 mg	0.5 mL
3 to <4	7 mg	0.7 mL
4 to <5	9 mg	0.9 mL

Table K. Dose of 4 mg/kg using RAL Oral Granules for Suspension 10 mg/mL

Weight Band (kg)	4 mg/kg	Volume (mL)
	Dose in (mg)	Volume to Administer
2 to <3	10 mg	1 mL
3 to <4	15 mg	1.5 mL
4 to <5	20 mg	2 mL

Table L. Dose of 5 mg/kg using RAL Oral Granules for Suspension 10 mg/mL

Weight Band (kg)	5 mg/kg	Volume (mL)
	Dose in (mg)	Volume to Administer
2 to <3	15 mg	1.5 mL
3 to <4	20 mg	2 mL
4 to <5	25 mg	2.5 mL

[figure not shown]
Table M. Dose of 1 mg/kg using RAL Oral Granules for Suspension 10 mg/mL

Weight Band (kg)	1 mg/kg	Volume (mL)
	Dose in (mg)	Volume to Administer
2 to <3	3 mg	0.3 mL
3 to <4	4 mg	0.4 mL
4 to <5	5 mg	0.5 mL

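### Appendix III Table I, labelled 6 mg/kg, gives more than 6 mg/kg per dose and more than 12 mg/kg/day at every weight it covers, and no passage says whether the Schema's limits apply to the labelled or the weight-band dose

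*Protocol*

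**What the plan says.** The Schema, Section 5.11 and Section 9.1 all set Cohort 2 dosing for Days 29 to 42 at 6.0 mg/kg twice daily. Directly after the regimen, the Schema allows dose modification between 1.5 and 6 mg/kg per dose and adds: "Dosing frequency may also be modified from once to twice daily, reaching a maximum daily dose of 12 mg/kg/day". This is the only daily maximum in the documents.

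Section 5.11 sends the reader to Appendix III for the dose in milligrams. The table for this step is headed "Table I. Dose of 6 mg/kg using RAL Oral Granules for Suspension 10 mg/mL", and the weight that selects its row is "Weight on Day 28-32 of Life Study Visit" (Section 5.11, Table 10). That weight is kept for the whole step. Tables G to I are in use; J to M are held for possible later changes.

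Two sentences link mg/kg doses to the tables: "Refer to Appendix III for dosing tables of RAL oral granules for suspension based on 1.5, 2, 3, 4, 5, and 6mg/kg" in Section 5.11 and "Dosing tables found in Appendix III will be used for dosing changes and are based on weight bands" in Section 6.2. Neither gives a rounding rule or a tolerance.

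In the body of the protocol the mg/kg range is tied to the first cohort: "RAL dosing in Cohort 1 may be modified in the range of 1.5 mg/kg to 6 mg/kg per dose" (Section 3.0, and likewise in Section 6.21). The Cohort 2 text in Sections 3.0 and 6.21 gives no mg/kg limit. Section 6.21 adds that the dose is raised linearly if the minimum PK targets are missed.

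**The concern.** A weight-band table can be expected to fall on both sides of its label. Table I falls on one side only: no infant it covers receives as little as 6 mg/kg at the reference weight. The planned regimen already equals the Schema maximum by its label, and it exceeds that maximum as dosed.

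Two things are at stake in a trial whose third primary objective is to determine a dose.

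- **The reported dose.** A regimen written up as 6 mg/kg twice daily would describe a dose that Table I never gives at the reference weight. Neither document plans a Cohort 2 summary of mg/kg given. SAP Section 4.5 summarises the percentage of days on drug, and PK is analysed outside the SAP. Protocol Tables 2 and 4 do report a mean mg/kg dose for the earlier paediatric study.
- **The linear-increase rule.** If the Schema figures govern Section 6.21, there is no room to increase in weeks 5-6, because the label is already at the top and the banded dose is above it. If they do not, nothing in Section 6.21 limits the increase. The documents do not say which applies.

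**Working it through.** **Inputs.** Doses and bands: Appendix III. Nominal regimen: Section 5.11. Limits: Schema. Reference weight: Section 5.11, Table 10.

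**The plan's own figure.** 2 doses x 6 mg/kg = 12 mg/kg/day, so the Schema maximum is exactly the labelled Days 29-42 regimen.

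**Table I.** Dose per kg = table dose / reference weight; daily dose = twice that. Each upper band limit is excluded.

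| Band (kg) | Dose | At lower limit | At midpoint | Towards upper limit | mg/kg/day | Midpoint excess over 6 |
|---|---|---|---|---|---|---|
| 2 to <3 | 20 mg | 20/2 = 10.0 | 20/2.5 = 8.0 | 20/3, so >6.67 | 20.0 to >13.33 | 33% |
| 3 to <4 | 25 mg | 25/3 = 8.33 | 25/3.5 = 7.14 | 25/4, so >6.25 | 16.67 to >12.5 | 19% |
| 4 to <5 | 30 mg | 30/4 = 7.5 | 30/4.5 = 6.67 | 30/5, so >6.0 | 15.0 to >12.0 | 11% |

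At the midpoints the daily dose is 16.0, 14.3 and 13.3 mg/kg/day. To receive exactly 6 mg/kg an infant would have to weigh 20/6 = 3.33, 25/6 = 4.17 or 30/6 = 5.0 kg. Each of these lies at or beyond the excluded top of its band, so the excess holds at every weight covered.

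**The other Appendix III tables, by the same division.**

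- Table G (1.5 mg/kg, in use): 2.0 to >1.33, 1.67 to >1.25, 1.75 to >1.40. It straddles its label in every band.
- Table H (3 mg/kg, in use): 4.0 to >2.67, 3.33 to >2.50, 3.75 to >3.0. It straddles in two bands and is above throughout 4 to <5 kg.
- Table L (5 mg/kg, reserve): 7.5, 6.67 and 6.25, each falling to >5.0. Above its label throughout.
- Table M (1 mg/kg, reserve): 1.5, 1.33 and 1.25, each falling to >1.0. Above its label throughout.

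Among the tables in use, only Table I is above its label in every band.

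**Is there a rounding rule?** 6 x the upper band limit = 18, 24 and 30 mg; rounded up to the next 5 mg this gives 20, 25 and 30 mg, as printed. Tables L and M equal label x upper limit exactly (15, 20, 25 and 3, 4, 5 mg). Tables G and H do not follow this: 1.5 x the upper limit is 4.5, 6 and 7.5 mg against 4, 5 and 7 mg printed; 3 x the upper limit is 9, 12 and 15 mg against 8, 10 and 15 mg. The pattern suggests deliberate rounding up in Table I, but no one rule fits all the tables.

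**Likely weights.** The documents give no weights at Day 28-32. Assume a gain of 0.5-1.5 kg on the Cohort 1 median birth weight of 3.02 kg (Section 1.29), so about 3.5-4.5 kg. The dose is then 6.25-7.5 mg/kg, which is 4-25% above the label, or 12.5-15 mg/kg/day. At 4.9 kg it is 30/4.9 = 6.12 mg/kg, 2% above.

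**Top of the table.** There is no row at 5 kg or more. The largest Cohort 1 birth weight was 4.20 kg; a gain of 5.0 - 4.20 = 0.80 kg, inside the same assumed range, takes such an infant off the table.

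**The case against.** The strongest reply is that the labels are nominal and everyone knows it. The tables are called weight-band tables, Section 5.11 says the aim is to keep dose adjustments few, and fixing a dose for an infant who is growing is a sensible reason to round up. The upward pattern in Tables L, M and the top band of H supports this. Protocol Table 6, the marketed dosing described as approximately 6 mg/kg, also gives 30 mg at 4 to <5 kg and so reaches 7.5 mg/kg. This makes intentional rounding the likely explanation. It does not settle the point: Table 6 says it is approximate and falls on both sides of 6 mg/kg (20 mg at 3 to <4 kg is 6.67 to >5.0; 30 mg at 4 to <6 kg is 7.5 to >5.0). Appendix III carries no such word.

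A second reply is that the Schema sentence concerns modification after interim analysis, not the planned regimen. That is correct. The Schema does word its figures as limits, but on modification; what is missing is whether they bind the label or the banded dose.

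A reader might infer more, and the documents do not support it:

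- **That infants are overdosed or Table I is a misprint.** No passage shows that the banded doses were unintended, and the arithmetic says nothing about which figure is right.
- **That PK target attainment is biased.** AUC and trough are measured under the doses given, so a loose label does not by itself distort them.
- **That doses near 20 mg/kg/day are to be expected.** That needs an infant of about 2 kg at four weeks, which is unlikely.
- **That Table I can be set against the 5.7 mg/kg mean in protocol Table 4.** That mean covers ages 4 weeks to <6 months, whereas these values are at one visit's reference weight; the two are not like for like.

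**Conclusion.** The point holds as a conflict between a label, a stated maximum and the table that sets the dose. At the reference weight the excess over 6 mg/kg runs from just above 0% near 5 kg to 67% at 2 kg (10.0/6), with 33%, 19% and 11% at the band midpoints. It is small near 5 kg, and it falls during the step because the dose is fixed while the infant grows. The one-sidedness rests on no assumption; only the 4-25% range depends on the assumed Day 28-32 weights.

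The consequences are limited to two: the reported regimen and the stated maximum do not describe the dose delivered, and it is unclear whether the Section 6.21 increase can act in weeks 5-6.

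The scope is infants dosed from Table I under Version 2.0, that is the Cohort 2 RAL-exposed group, with a minimum of 8 evaluable infants. Tables A to F were removed, so what the Version 1.0 infants received cannot be checked here.

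**What to change.** Reconcile the Schema limits, the Section 5.11 regimen and Table I. State whether 6 mg/kg per dose and 12 mg/kg/day apply to the labelled dose or to the weight-band dose given, and whether they govern the Section 6.21 increase. If the bands are meant to round up, state the rule in Appendix III. Which figure stands is for the clinical team.

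Separately, reconcile the absence of a Table I row for infants of 5 kg or more at the Day 28-32 visit with the instruction to dose from that weight.

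In the Cohort 2 PK and safety reports, summarise the mg/kg given (milligram dose divided by reference weight) beside the nominal label.

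The cost is a protocol clarification and one derived variable. The reference weight is already measured at the visit, and it fixes the milligram dose.
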